### 3.1.1 Dose Limiting Toxicity

The following assessment guidelines for the management of dose limiting toxicity (DLT) are intended to ensure the safety of each patient while on the study. The descriptions and grading scales found in the revised NCI Common Terminology Criteria for Adverse Events (CTCAE) version 4.0 will be utilized for AE and DLT reporting. All appropriate treatment areas should have access to a copy of the CTCAE version 4.0. A copy of the CTCAE version 4.0 can be downloaded from the CTEP web site ([http://ctep.cancer.gov/protocolDevelopment/electronic\\_applications/ctc.htm#ctc\\_40](http://ctep.cancer.gov/protocolDevelopment/electronic_applications/ctc.htm#ctc_40)).

All adverse events will be classified as follows for determination of relatedness to AdHER2 vaccination:

- Unrelated
- Unlikely
- Possibly related
- Probably related
- Definitely related

For the purposes of this study, the definitions of dose limiting-toxicities include:

- CTCAE Grade 2 and greater allergic reactions
- CTCAE Grade 2 and greater autoimmune disorders
- CTRCD, defined as a decrease in the LVEF of > 10 percentage points, to a value in < 53%. Documentation of the above specified change in LVEF will require cardiac consultation for determination of clinical significance. Cardiac function deterioration clinically associated with apparent cardiotoxic agent use after off-therapy will be censored at the point of cardiotoxic agent use.
- CTCAE Grade 3 or greater organ toxicity (dermatologic, gastrointestinal, hepatic, pulmonary, renal/genitourinary, or neurologic) occurring within 30 days of vaccine administration that are at least possibly related to research in.

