 Clinical labs CBC with differential, PT/PTT, acute care panel, hepatic panel, mineral panel, total protein, amylase/lipase, uric acid, lipid panel.

 Tumor markers are optional and will be tested dependent on the primary sites. Patients with primary breast, ovarian and GI tract cancer might be tested for CA 125, CA 15-3, CA19-9, CA 27-29, and CEA. Other organ specific tumor markers can be tested

 Only until 12 weeks after the last dose of vaccination.

 Research bloods will not be used in data analysis if the patient has started on any treatment that can affect the data of the study. Week 40 and after samples will only be collected if the patient has not progressed (PD).

 This is optional and to be performed if clinically indicated. If the patient received scans within 30 days of enrollment at an outside institution the patient will not be required to have a second scan performed. Instead, the baseline scan will be used to collect target lesions.

 If the patient received scans within 30 days of enrollment at an outside institution the patient will not be required a screening scan to consent. Instead, the baseline scan will be used to identify target lesions. If the patient has bone metastasis and clinically indicated, a bone scan will be done at restaging.

 If the patient received scans within 30 days of enrollment at an outside institution the patient will not be required to have a second scan performed. Instead, the baseline scan will be used to collect target lesions. If a confirmatory scan is performed in less than 8 weeks from prior CT, the interval of CT follow-up will be adjusted to maintain 8 weeks interval to avoid unnecessary radiation exposure. For bladder cancer adjuvant indication, CT scans every 12 weeks during first 12 month, every 16 weeks for the next 12 months and at the end of study if no recurrence.

 Optional documentation on cardiac function will be collected once a patient is on study but off treatment for the purposes of long-term assessment of the impact of AdHER2 vaccination on cardiac function. Note: if the patient had an echo within 30 days of enrollment at an outside institution the patient will not be required a screening echo to consent. Instead, the baseline echo will be performed at NIH prior to treatment and used to identify target lesions.

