 Dose can be delayed up to 8 weeks. The study will reset at the time of study resumption. For example, if dose at week 8 is delayed and resumed at original week 11, that week 11 will now be considered week 8.

 If there is a need for confirmatory scans based on the result of Week 48 evaluation, additional visit will occur at week 52 which will include clinical assessment with physical exam and laboratory assessment.

 Patients who progress do not require a full evaluation. Only physical exam, clinical labs, echocardiogram and AE reports will be required.

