#### 3.5.1 Criteria for Removal from Protocol Therapy

- 3.5.1.1 Completion of protocol therapy (receipt of 5 doses of autologous AdHER2 DC vaccine).
- 3.5.1.2 Disease progression per **6.2, Response Criteria**. Note Exception: Clinically stable patients with PD at Weeks 8, 16 or 24 re-staging will be allowed to remain on protocol therapy per PI's discretion.
- 3.5.1.3 Patient experiences a dose limiting toxicity as outlined in Section **3.1.1**.
- 3.5.1.4 Patient experiences a Grade 3 or greater adverse event/toxicity *not* described in Section **3.1.1** that is deemed by the Principal Investigator as possibly, probably or definitely related to AdHER2 DC vaccination.
- 3.5.1.5 Patient experiences unresolved treatment-related toxicity.
- 3.5.1.6 Diagnosis of a secondary malignancy other than superficial basal cell or squamous cell carcinoma of the skin.
- 3.5.1.7 The patient experiences a treatment delay of more than 8 weeks from the scheduled target date for receipt of AdHER2 DC vaccine.
- 3.5.1.8 Inter-current illness or medical circumstance that in the opinion of the Principal Investigator unacceptably increases the risk of treatment. This applies to the conditions related to the cancer diagnosis that led to the enrollment in current study.
- 3.5.1.9 The patient is non-compliant with study requirements.
- 3.5.1.10 The patient becomes too ill to return for protocol specified study visits.
- 3.5.1.11 The patient becomes pregnant during the study.
- 3.5.1.12 The patient requests to be withdrawn and refuses further therapy.
- 3.5.1.13 The patient requires a prohibited concomitant medication.
- 3.5.1.14 Death

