3.5.2 Continued Monitoring for Potential Cardiac Toxicity Once Off Protocol Therapy

- 3.5.2.1 Patient is removed from therapy for reasons outlined in Section **3.5.1**.
- 3.5.2.2 Patient will continue to undergo designated cardiac monitoring studies at subsequent study weeks as outlined in **Figure 11**.
- 3.5.2.3 Cardiac troponin levels (Weeks 0, 4, 8, 12, 16, 20, 24, 28, 32, 40 and 48) and echocardiograms (Weeks 4, 12, 20, 28, 32, 40, 48, 60, 76, 100 and 124) including HPE and ECOG assessments.
- 3.5.2.4 Cardiac monitoring will be performed either *at the NIH or through the patient's LMD*. For patients who come off-treatment for disease progression or other reasons, every effort will be made to capture ongoing documentation on cardiac function as is reasonably practicable, to allow long-term assessment of the impact of AdHER2 vaccination on cardiac function.

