### **3.5.3 Off Study Criteria**

- 3.5.3.1** Completion of scheduled study visits.
- 3.5.3.2** PI decision to end the study.
- 3.5.3.3** Patient requests to be withdrawn and refuses further study participation.
- 3.5.3.4** The patient is non-compliant with study requirements.
- 3.5.3.5** The patient becomes too ill to return for protocol specified study visits.
- 3.5.3.6** Documentation of rapid disease progression or clinical deterioration between the screening (including outside information) and baseline evaluations. These patients will be removed from study and precluded from receiving AdHER2 DC vaccination.
- 3.5.3.7** If a patient begins to take a known cardiotoxic agent the patient will come off study and we will not use data after that point.

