### 12.4 EVALUATION OF BENEFITS AND RISKS/DISCOMFORTS

The AdHER2 DC vaccine being given in this study targets both the extracellular (EC) and transmembrane TM domains of the HER2 protein receptor. The goal of therapeutic vaccination with this product is to stimulate the patient’s own immune system to make *polyclonal antibodies* (and also potentially killer cells) that recognize HER2. It is hoped that that these antibodies will have a similar beneficial effect in controlling disease and potentially prolonging survival.

Use of trastuzumab in women with breast cancer has been shown to be associated with a small, but significant risk (about 7%) for developing cardiac dysfunction. It is usually observed in patients who have previously received chemotherapy that is known to affect the heart. The risk of cardiac dysfunction is greater (about 27%) when trastuzumab is given in combination with anthracycline chemotherapy drugs such as doxorubicin (Adriamycin) and cyclophosphamide (Cytoxan). Exactly how trastuzumab causes cardiac toxicity is unknown. It is also not known whether antibodies made by a person’s own immune system will cause cardiac dysfunction. Because of this, cardiac function will be monitored very closely while receiving the vaccine treatment and for 24 months following the last dose of vaccine. In addition, there are strict stopping rules included in this study for any signals of cardiac toxicity that would appear to be exceeding the 7% frequency observed with trastuzumab monotherapy. There are currently multiple clinical trials with vaccines using different platforms and approaches to target HER2 and to date there have been no reports of significant vaccine-associated cardiac toxicity.

The only other likely risk associated with receiving this vaccine is local injection site reactions i.e. discomfort, itching, redness, swelling, or soreness/pain at the site where the vaccine is injected into the skin. In addition, due to the proposed mechanism of action that includes a possible acute inflammatory response at focal sites of tumor, subjects may experience discomfort at sites of metastatic disease and/or acute reactive pleural or peritoneal effusions. There is a more remote potential for systemic symptoms such as fatigue, malaise or fever associated with vaccination but these are much less likely because patients are being given their own cells that have been transduced to express HER2. The AdHER2 vector used to transduce the patient’s

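### Off-treatment echocardiograms are optional in one place and required in others, and LVEF data after a cardiotoxic agent fall under two different rules

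*Combined protocol and SAP*

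**What the plan says.** **Echocardiograms once treatment has ended.** Footnote 15 in Section 3.4 is attached to the 2-D echocardiogram row: "Optional documentation on cardiac function will be collected once a patient is on study but off treatment for the purposes of long-term assessment". Elsewhere the same assessments are described differently:

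- Section 3.5.2.2, for a patient off therapy: "Patient will continue to undergo designated cardiac monitoring studies at subsequent study weeks as outlined in" Figure 11.
- Section 3.5.2.4, for patients who stop treatment for progression or other reasons: "every effort will be made to capture ongoing documentation on cardiac function as is reasonably practicable".
- Footnote 18, attached to Weeks 60, 76, 100 and 124, for patients who have progressed: "Only physical exam, clinical labs, echocardiogram and AE reports will be required".
- Section 12.4: "cardiac function will be monitored very closely while receiving the vaccine treatment and for 24 months following the last dose of vaccine". Section 12.5 repeats this, and Section 1.2.1.2 describes LVEF follow-up for at least two years after the last dose.

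Section 3.5.1.1 lists among the reasons for leaving therapy "Completion of protocol therapy (receipt of 5 doses of autologous AdHER2 DC vaccine".

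**Data after a cardiotoxic agent.** Section 3.1.1 says: "Cardiac function deterioration clinically associated with apparent cardiotoxic agent use after off-therapy will be censored at the point of cardiotoxic agent use". Section 3.5.3.7 says: "If a patient begins to take a known cardiotoxic agent the patient will come off study and we will not use data after that point". Section 1.2.1.2 also takes patients on CT agents off study; I read CT as cardiotoxic.

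**Where these data are used.** The fraction with cardiac dysfunction is a primary objective (Section 1.1.1). The Précis gives 48 weeks for the primary endpoints and extended LVEF follow-up to 30 months. Section 11 sets 7% as the acceptable ceiling, and Section 11.3 reports the fraction with 80% and 95% confidence intervals.

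**The concern.** An LVEF fall enters the cardiac fraction only if the echocardiogram is done and its result is used. The protocol is inconsistent on both.

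If off-treatment echocardiograms are optional, whether one exists may depend on progression, symptoms or convenience, so gaps are unlikely to be random. Section 12.5 stresses that a vaccine-induced immune response cannot be withdrawn and relies on picking up late as well as early signals. The off-treatment period therefore carries part of the primary safety question.

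If two data rules are available after a cardiotoxic agent, the number of events can depend on which is applied. In an open-label, single-arm study that choice could be made with the LVEF results in view. Under Section 3.1.1 the censoring is triggered by the fall itself and by a judgement about its cause.

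**Working it through.** **1. How many echocardiograms footnote 15 reaches.** Section 3.5.2.3 lists Weeks 4, 12, 20, 28, 32, 40, 48, 60, 76, 100 and 124: 11 post-baseline. The last planned dose is at Week 24, and receiving it is removal from therapy (Section 3.5.1.1).

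- After Week 24: Weeks 28, 32, 40, 48, 60, 76, 100 and 124, so 8/11 = 73%.
- Due by Week 48: 7. Of these, Weeks 28, 32, 40 and 48 come after Week 24, so 4/7 = 57%.
- For a patient who stops after the Week 8 dose: 10 of 11.

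For Weeks 28 to 48 the conflict is between footnote 15 and Section 3.5.2.2. For Weeks 60 to 124 footnote 18 adds a second direct conflict, for progressed patients.

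**2. The two cardiotoxic-agent rules side by side.**

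| Patient who starts such an agent after therapy | Section 3.1.1 | Section 3.5.3.7 |
|---|---|---|
| LVEF falls, attributed to the agent | censored at agent use | later data unused |
| LVEF falls, judged unrelated to the agent | counted | later data unused |
| No fall | not addressed; nothing in it ends follow-up | follow-up ends |

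The rules agree on the first row and differ on the other two. In a simple fraction the third row changes nothing in the numerator. It could change the denominator, because the documents define neither an evaluable patient for the cardiac endpoint nor the handling of missing echocardiograms.

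**3. The plan's own figure.** Section 11.3 gives 6% and 85% for 3 or more of 30 at true rates of 3% and 15%. With

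P(X ≥ 3) = 1 − Σ(k = 0 to 2) C(30,k) p^k (1 − p)^(30 − k),

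I obtain 0.060 at p = 0.03 and 0.849 at p = 0.15. Both figures reproduce. They presume that every patient's cardiac outcome is known.

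**4. Illustration of uncounted events (assumed).** The documents give no ascertainment rate. Let s be the share of true events that are seen and counted, with 30 kept as denominator, so that p = 0.15 × s:

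| s | p | P(3 or more of 30) |
|---|---|---|
| 1.0 | 0.150 | 0.849 |
| 0.9 | 0.135 | 0.790 |
| 0.8 | 0.120 | 0.715 |
| 0.7 | 0.105 | 0.623 |
| 0.5 | 0.075 | 0.393 |

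**5. Illustration of the two rules (assumed).** Let c be the share of patients who start a cardiotoxic agent, half of their events come after the start, and q be the share of those late falls attributed to the agent. Then p = 0.15 × (1 − 0.5c) under Section 3.5.3.7 and p = 0.15 × (1 − 0.5cq) under Section 3.1.1.

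| c | 3.5.3.7 | 3.1.1, q = 0 | 3.1.1, q = 0.5 | 3.1.1, q = 1 |
|---|---|---|---|---|
| 0.2 | 0.790 | 0.849 | 0.821 | 0.790 |
| 0.4 | 0.715 | 0.849 | 0.790 | 0.715 |
| 0.6 | 0.623 | 0.849 | 0.755 | 0.623 |

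Entries are P(3 or more of 30). The same patients give different answers unless every late fall is attributed to the agent. Section 3.5.3.7 never counts more events than Section 3.1.1. Falls caused by the agent itself are not modelled; any that were judged unrelated and counted would raise the fraction.

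**The case against.** **Footnote 15 may be about paperwork.** It speaks of documentation, and its purpose clause resembles Section 3.5.2.4, which allows monitoring through the patient's own physician. Where the calendar makes a test optional, as with tumor markers, it says so of the test. The echocardiogram row also runs to Week 124. This is a possible reading, but the footnote sits on the echocardiogram row, and best effort, optional and required remain three different instructions. Section 3.3 follows patients with a cardiac DLT to Week 124, but that does not help detect a first late fall.

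**Section 3.5.3.7 may simply prevail.** Applied literally, it leaves Section 3.1.1 no later data to act on, and outcome-dependent censoring does not arise. That is fair, but no text gives it precedence.

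**Stronger readings that the documents do not support:**

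- A reader might infer that Section 3.1.1 lowers the fraction by a definite amount relative to Section 3.5.3.7; two attributed falls in 30 would be 6.7 percentage points. Both rules lose those same two events, so the figure does not separate them.
- A reader might treat all eight later echocardiograms as primary-endpoint data. Weeks 60 to 124 are extended follow-up; the primary-period count is 4 of 7.
- A reader might expect resumed trastuzumab in Part II to drive the problem. The documents do not say which therapies follow.
- A reader might think dose escalation rests on the late echocardiograms. Section 3.1.2 ties it to at least 3 of 6 patients reaching Week 12.

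**Conclusion.** The concern holds as two inconsistencies in the current text. First, off-treatment echocardiograms have no single status, and this touches 8 of the 11 scheduled after baseline and 4 of the 7 due by Week 48. If footnote 15 were followed literally, the later part of the primary cardiac fraction and the 24-month monitoring statements could lack data. Second, Sections 3.1.1 and 3.5.3.7 treat LVEF data after a cardiotoxic agent differently for falls judged unrelated and for patients without a fall. If Section 3.1.1 governs, censoring depends on the outcome and on attribution.

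The counts come directly from the protocol. The probabilities of 0.715 and 0.393 rest on assumed losses of 20% and 50% of events and show sensitivity only. The documents do not say how many echocardiograms will be missed, how many patients will start such agents or how falls will be attributed, so neither the size nor the net direction of the effect can be fixed.

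**What to change.** 1. Reconcile footnote 15 with Sections 3.5.2.2 and 3.5.2.4, footnote 18, and Sections 12.4 and 12.5, so that off-treatment echocardiograms have one status throughout. If they remain optional, limit the cardiac conclusion and the 24-month monitoring statements to match.
2. Reconcile Sections 3.1.1 and 3.5.3.7 into one data rule that depends neither on the LVEF result nor on attribution.
3. Report a sensitivity fraction that counts every LVEF fall actually observed, including any recorded after a cardiotoxic agent was started.

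Whether monitoring continues after such an agent is for the sponsor to decide when reconciling the passages. The cost is a wording amendment, one added analysis row and a possibly less favourable cardiac fraction.

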### 3.5 CRITERIA FOR REMOVAL FROM PROTOCOL THERAPY AND OFF STUDY CRITERIA

Prior to removal from study, effort must be made to have all subjects complete a safety visit approximately 30 days following the last dose of study therapy.

#### 3.5.1 Criteria for Removal from Protocol Therapy

- 3.5.1.1 Completion of protocol therapy (receipt of 5 doses of autologous AdHER2 DC vaccine).
- 3.5.1.2 Disease progression per **6.2, Response Criteria**. Note Exception: Clinically stable patients with PD at Weeks 8, 16 or 24 re-staging will be allowed to remain on protocol therapy per PI's discretion.
- 3.5.1.3 Patient experiences a dose limiting toxicity as outlined in Section **3.1.1**.
- 3.5.1.4 Patient experiences a Grade 3 or greater adverse event/toxicity *not* described in Section **3.1.1** that is deemed by the Principal Investigator as possibly, probably or definitely related to AdHER2 DC vaccination.
- 3.5.1.5 Patient experiences unresolved treatment-related toxicity.
- 3.5.1.6 Diagnosis of a secondary malignancy other than superficial basal cell or squamous cell carcinoma of the skin.
- 3.5.1.7 The patient experiences a treatment delay of more than 8 weeks from the scheduled target date for receipt of AdHER2 DC vaccine.
- 3.5.1.8 Inter-current illness or medical circumstance that in the opinion of the Principal Investigator unacceptably increases the risk of treatment. This applies to the conditions related to the cancer diagnosis that led to the enrollment in current study.
- 3.5.1.9 The patient is non-compliant with study requirements.
- 3.5.1.10 The patient becomes too ill to return for protocol specified study visits.
- 3.5.1.11 The patient becomes pregnant during the study.
- 3.5.1.12 The patient requests to be withdrawn and refuses further therapy.
- 3.5.1.13 The patient requires a prohibited concomitant medication.
- 3.5.1.14 Death

3.5.2 Continued Monitoring for Potential Cardiac Toxicity Once Off Protocol Therapy

- 3.5.2.1 Patient is removed from therapy for reasons outlined in Section **3.5.1**.
- 3.5.2.2 Patient will continue to undergo designated cardiac monitoring studies at subsequent study weeks as outlined in **Figure 11**.
- 3.5.2.3 Cardiac troponin levels (Weeks 0, 4, 8, 12, 16, 20, 24, 28, 32, 40 and 48) and echocardiograms (Weeks 4, 12, 20, 28, 32, 40, 48, 60, 76, 100 and 124) including HPE and ECOG assessments.
- 3.5.2.4 Cardiac monitoring will be performed either *at the NIH or through the patient's LMD*. For patients who come off-treatment for disease progression or other reasons, every effort will be made to capture ongoing documentation on cardiac function as is reasonably practicable, to allow long-term assessment of the impact of AdHER2 vaccination on cardiac function.

### **3.5.3 Off Study Criteria**

- 3.5.3.1** Completion of scheduled study visits.
- 3.5.3.2** PI decision to end the study.
- 3.5.3.3** Patient requests to be withdrawn and refuses further study participation.
- 3.5.3.4** The patient is non-compliant with study requirements.
- 3.5.3.5** The patient becomes too ill to return for protocol specified study visits.
- 3.5.3.6** Documentation of rapid disease progression or clinical deterioration between the screening (including outside information) and baseline evaluations. These patients will be removed from study and precluded from receiving AdHER2 DC vaccination.
- 3.5.3.7** If a patient begins to take a known cardiotoxic agent the patient will come off study and we will not use data after that point.

#### **3.5.3.8 Death**

### **3.5.4 Off Protocol Therapy and Off Study Procedure**

All subjects must be taken off study through the NCI Central Registration Office CRO). Authorized staff must notify CRO when a subject is being taken off protocol therapy and when a subject is taken off-study. A Participant Status Updates Form the web site (<http://home.ccr.cancer.gov/intra/eligibility/welcome.htm>) main page must be completed and sent via encrypted email to: NCI Central Registration Office [[contact]](mailto:[contact]).

